Protocol of a Thesis for Partial Fulfillment of M.D. degree in Anesthesia

Title:

Preoperative Evaluation of IVC Collapsibility Index and Caval Aorta Index for Prediction of Hypotension after Induction of General Anesthesia in patients Undergoing Craniotomy Surgeries

Postgraduate Student: **[name]**

Degree: *M.B.B.CH- assistant-lecturer in department of Anesthesia, Intensive Care and Pain Management- Faculty of Medicine -Ain Shams University*

Supervisor: **[name]. [name]**

Academic Position: *Professor of Anesthesia, Intensive Care and Pain Management*

Department: *Anesthesia, Intensive Care and Pain Management - Faculty of Medicine Ain Shams University*

Co- Supervisor: **Ass.[name]. [name]**

Academic position: *Assistant Professor of Anesthesia, Intensive Care and Pain Management*

Department: *Anesthesia, Intensive Care and Pain Management - Faculty of Medicine Ain Shams University*

Co- Supervisor: **[name] [name]**

Academic position: *lecturer of Anesthesia, Intensive Care and Pain Management*

Department: *Anesthesia, Intensive Care and Pain Management - Faculty of Medicine Ain Shams University*

Co- Supervisor: **[name] [name]**

Academic Position: *lecturer of Anesthesia, Intensive Care and Pain Management*

Department: *Anesthesia, Intensive Care and Pain Management - Faculty of Medicine Ain Shams University*

**Faculty of Medicine
Ain Shams University
2023**

What is already known on this subject? AND What does this study add?

Intraoperative hypotension has been the most frequent side effect after anesthesia, with an incidence of 15.3% to 33%. Hypotension can be severe (incidence 5.4%) and may cause systemic hypoperfusion and ischemic events. (Jor, O., Maca J., Koutna J., et al.2018)

The caval aorta index (IVC/Ao) compares the maximum diameter of the IVC with the abdominal aorta (Ao).

This study is to assess the accuracy, repeatability, and reproducibility of preoperative evaluation of IVC Collapsibility Index and Caval Aorta Index for prediction of hypotension after induction of general anesthesia.

1. INTRODUCTION

Post- anesthesia hypotension is of common occurrence, and it hampers tissue perfusion. The magnitude of hypotension is determined by the preoperative volume status, which varies depending on ASA physical status, preoperative comorbidities, preoperative medications, and fasting. (Bajawa S, Jindal R, Kulshrestha A. 2013)

Intraoperative hypotension may solely be responsible for unfavorable consequences during or after surgery, including myocardial infarction, stroke, acute kidney injury, extended hospital stay, and higher death rates after one year in both cardiac and non-cardiac operations. (Monk TG, Saini V, Weldon BC, et al. 2005)

General anesthesia causes significant alterations in hemodynamics, as both inhalational and intravenous anesthetics cause bradycardia, decrease in systemic vascular resistance and vasodilatation, and decrease in myocardial contractility, cardiac output and stroke volume, with the absence of surgical stimulus, making induction of anesthesia is the most crucial period at which hypotension occurs. There are non-modifiable factors for post general anesthesia hypotension as ASA III & IV, old age, and the inevitable use of propofol and fentanyl, however there are modifiable factors and preoperative intravascular volume is one of the most important of them. (Kouz K, Hoppe P, Briesenick L, et al, 2020)

There is no uniform definition for intra-operative hypotension. It even remains unknown whether intra-operative hypotension should be defined based on absolute arterial pressure thresholds or on relative thresholds considering a decrease from

baseline arterial pressure. Frequently used definitions include systolic arterial pressure below 80 mmHg, a decrease in systolic arterial pressure of more than 20% below baseline, and a combination of definitions consisting of an absolute SAP below 100 mmHg and/or 30% decrease below baseline. (**Saugel B, Reuter DA, Reese PC, 2017**).

Due to different definitions of hypotension and diverse patient populations, the effect of volume preload on prevention of hypotension is still controversial. Many recommendations to identified sonographic determination of inferior vena cava (IVC) collapsibility index (IVCCI) as non-invasive, and easy technique for evaluating volume status. Recent guidelines from the American Society of Echocardiography support the general use of IVCCI in assessing volume status. (**Dipti A, Soucy Z, Surana A, et al 2017**)

The etiology of intra-operative hypotension is multifactorial. Intra-operative hypotension can, among other factors, be caused by vasodilation (anaesthetic drugs, systemic inflammation), intravascular hypovolaemia (bleeding), low cardiac output (bradycardia or low stroke volume), high intra-thoracic pressure (mechanical ventilation), impairment of sympathetic nervous system or compromised baroreflex regulation. (**Kouz K, Hoppe P, Briesenick L, et al, 2020**).

With some individual variation, autoregulation of cerebral blood flow (CBF) typically occurs within a mean arterial pressure (MAP) range of 60 to 150 mmHg. Outside of this range, the brain is unable to compensate for changes in perfusion pressure, and the cerebral blood flow (CBF) increases or decreases passively with corresponding changes in pressure, resulting in the risk of ischemia at low pressures and edema or hemorrhage at high pressures. We aim for a MAP above the lower limit of autoregulation. (**Lassen NA**.)

2.AIM /OBJECTIVES

- **Primary aim:** Assessment of the accuracy, repeatability, and reproducibility of preoperative evaluation of IVC collapsibility index and Caval Aorta Index for prediction of hypotension after induction of general anesthesia.
- **Secondary aim:** to compare values of both IVCCI and Aorto-Caval Index in prediction of post general anesthesia induction hypotension.

3.METHODOLOGY:

Subjects and Methods

- **Type of Study:** Prospective cohort study.
- **Study Setting:** the study will be conducted at Ain-Shams University Hospitals.
- **Study Period:** the study will take place till reaching the target sample size.
- **Study Population:**

Selection criteria:

Inclusion Criteria:

- Patients aging 18-40 years.
- $BMI < 40 \text{ kg/m}^2$.
- ASA I, II.
- Fasted according to the ASA guidelines: 2 hours for clear fluids, 6 hours after light meal, 8 hours after a full meal with high calorie or fat content.
- Scheduled for elective craniotomy surgeries before induction of general anesthesia.

- Exclusion Criteria:

- Patients < 18 or > 40 years.
- $BMI > 40 \text{ kg/m}^2$.
- ASA III, IV.
- Current or recent pregnancy (within 3 months).
- Pre-existing cardiac disease or hypertension.
- On medications affecting blood pressure (BBs, CCBs,..).
- Refusing to undergo the study.

- **Sample Size Calculation:**

Using PASS 11 program for sample size calculation ; setting power at 80% , error at 5%, incidence of hypotension among patients undergoing general anesthesia at 78.43% (**Omar et al.,2023**), and sensitivity and specificity of ultrasound guided Aorto-Caval index (IVC-AO) for prediction post general anesthesia hypotension at 77.5% and 63.6% , respectively, (**Omar et al.,2023**) , so a sample size of 32 patients undergoing craniotomy surgeries under general anesthesia will be needed.

Assuming that a drop out is of 10% , a sample size of at least 36 patients undergoing craniotomy surgeries under general anesthesia will be needed.

- **Ethical Consideration:**

- Approval from the research Ethics committee of faculty of medicine ,Ain shams university is mandatory and will be obtained before start in this study.
- Obtaining an informed consent: Written signed and dated informed consent will be obtained from patients or legal guardian of each participant before being entered into the study.
- Patients can withdraw from the study at any time and still get the full medical service within the facility. patients can refuse to participate and still get the standard care.
- Patients, privacy and confidentiality with the right to know the research results are ensured.

- **Sample size:** 40 cases

- **Study Tools:** Ultrasound curvilinear array, low - frequency (2- 5 MHz)

- **Study Procedure**

Pre-operative: All patients will be subjected to:

1- Detailed medical history taking with special emphasis on:

- History of cardiac disease or anti-hypertensive medications.
- Demographic data (age, sex, weight, height, body mass index).

2- Thorough clinical examination including:

- General and local examination.
- American Society of Anesthesiologists (ASA) physical status classification.

3- Laboratory investigations:

- Complete blood picture (CBC).
- Prothrombin time (PT), INR and activated partial thromboplastin time (aPTT).

- Liver functions tests.
- Cardiac enzymes.
- Kidney function tests.

4- Electrocardiogram (ECG).

Intra-operative:

- On the day of surgery, pre-operative fasting for 8 hours will be confirmed.
- Upon arrival to the operating room, routine monitors in the form of pulse oximetry, electro-cardiogram and non-invasive blood pressure monitors will be applied. Intravenous line will be secured.
- central venous line and invasive arterial line will be applied.
- Systolic blood pressure, diastolic blood pressure, MAP, and HR at baseline will be recorded.
- After obtaining informed consent, the patient is placed in the supine position with the head of the bed elevated 30 degrees.
- The ultrasound transducer is placed in the right subcostal position to visualize the IVC.
- The maximum (expiratory) and minimum (inspiratory) IVC diameters are measured.
- The IVCCI is calculated using the following formula:

$$\text{IVCCI} = (\text{maximum IVC diameter} - \text{minimum IVC diameter}) / \text{maximum IVC diameter} * 100$$

- To the left of the IVC, the abdominal aorta is visualized 10 mm above the coeliac trunk.
- The aortic diameter is measured at maximum diameter during systole
- The IVC : Ao index will be derived by taking the ratio of the maximum IVC diameter during expiration and the maximal abdominal aortic diameter during systole.
- The IVC/Ao index is calculated using the following formula:

$$\text{IVC/Ao index} = \text{IVC diameter} / \text{aortic diameter}.$$

- The measurements are repeated three times and the average is calculated.(Finnerty NM, Panchal AR , Boulger C, et al 2017)

- The patients will be induced as per a standard protocol. They will be given midazolam $0.05\text{--}0.1 \text{ mg} \cdot \text{kg}^{-1}$, and fentanyl $2\text{--}3 \text{ } \mu\text{g} \cdot \text{kg}^{-1}$ before

induction. Patients will be induced with propofol $1-2 \text{ mg.kg}^{-1}$, till loss of response to verbal commands. They will then mask ventilated with 100% oxygen and isoflurane 1.0%–1.2%. Atracurium (0.5 mg.kg^{-1}) will be given for muscle relaxation. Three minutes after atracurium, patients will be intubated by performing a gentle and quick laryngoscopy lasting not more than 15 s. In males, 8 mm or 8.5 mm internal diameter endotracheal tube will be used. In females, 7 mm or 7.5 mm internal diameter endotracheal tube will be used. (Chowdhury SR, Datta PK, Maitra S, et al, 2023)

- Measurement tools - Mean arterial blood pressure will be measured in supine position in one of the upper limbs in the operating room at 1-minute intervals starting from the baseline preoperative reading until skin incision as follows: 1-minute post-induction reading, 2-minutes post-induction reading, pre-intubation reading & post-intubation readings until skin incision. Taking in consideration that the maximum time for recording the readings of the blood pressure is 15 minutes because if hypotension occurred after this time it is unlikely to be due to the effect of induction of anesthesia.
- Heart rate will be recorded at 1-minute intervals starting from the baseline pre-operative reading until skin incision as follows: 1-minute post-induction reading, 2-minutes post-induction reading, pre-intubation reading & post-intubation readings until skin incision. Any episode of hypotension (defined as mean arterial pressure $< 80\%$ of the baseline reading or MAP less than 60 mmHg) will be managed by ephedrine 5 mg every 2 min to increase SBP to 80% of the baseline or MAP more than 70 mmHg. If the hypotensive episode persisted for 2 minutes, another bolus of norepinephrine will be administered.
- The strength of the association between different parameters and post-anesthesia hypotension was calculated. To find out the value of the optimal cut-off for the prediction of post-anesthesia hypotension.

● Statistical Method:

Data collection: Demographic, clinical data, investigations, imaging, ECG and echocardiographic data will be obtained and recorded in special registration form.

Statistical analysis:

Statistical data will be tabulated, and Statistical analysis is to be performed using the latest available version of SPSS.

4. REFERENCES:

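### The primary aim names reproducibility separately from repeatability, but the protocol provides for no readings by another operator, on another occasion or by independent re-reading

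*Protocol*

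**What the plan says.** Under 2. AIM/OBJECTIVES, the primary aim is "Assessment of the accuracy, repeatability, and reproducibility of preoperative evaluation of IVC collapsibility index and Caval Aorta Index" for predicting hypotension after induction. The opening summary of what the study adds says the same: "This study is to assess the accuracy, repeatability, and reproducibility of preoperative evaluation of IVC Collapsibility Index and Caval Aorta Index". In both places repeatability and reproducibility are listed as two properties, next to accuracy. The secondary aim compares the two indices as predictors.

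The ultrasound examination is set out once, under Study Procedure (Intra-operative), between the baseline haemodynamic readings and the description of induction. For the vena cava, "The ultrasound transducer is placed in the right subcostal position to visualize the IVC". The aorta is then visualised, the two indices are derived, and "The measurements are repeated three times and the average is calculated". The text does not say who takes the readings.

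Sample Size Calculation works from an incidence of hypotension of 78.43% and from "sensitivity and specificity of ultrasound guided Aorto-Caval index (IVC-AO) for prediction post general anesthesia hypotension at 77.5% and 63.6"%. The analysis is described at the end of the measurement section, where "The strength of the association between different parameters and post-anesthesia hypotension was calculated", followed by a search for the optimal cut-off. Statistical Method adds only data recording, tabulation and the software.

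**The concern.** In the usual measurement sense, repeatability is agreement among readings taken under the same conditions. Reproducibility is agreement when a condition such as the operator or the occasion changes. A primary aim that names both needs both kinds of reading, and the procedure describes only repeats, with no change of condition.

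Two things are at stake. A named part of the primary aim would go unanswered. And at reporting, agreement among the three repeats might be offered as evidence of reproducibility because it is the only agreement available.

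This is not a complaint that an analysis method is missing. The choice of agreement statistic can be left to an analysis plan. Who measures, and when, is study procedure and has to be fixed before induction takes place.

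**Working it through.** The protocol states no figure for reproducibility, so there is none to reproduce. The check sets the aim against the rest of the text.

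**1. What each part of the aim needs, and what is described**

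| Part of the primary aim | Data needed | Provided for in the protocol |
|---|---|---|
| Accuracy | Index values before induction, and hypotension status after it | Yes: Study Procedure, with blood pressure at 1-minute intervals and a definition of hypotension |
| Repeatability | Repeat readings under the same conditions | Repeats are described, then averaged; operator not stated |
| Reproducibility | Readings under a changed condition: another operator, another occasion or an independent re-reading | None described |

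Study Tools lists one transducer type. No section mentions a second session, a second reader or stored images for re-reading. Procedures described that yield readings under changed conditions: 0.

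**2. Does the sample size point to a reproducibility component?**

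The inputs listed are power 80%, error 5%, incidence 78.43%, sensitivity 77.5%, specificity 63.6% and dropout 10%. The stated 32 can be obtained from these if a null sensitivity of 50% is assumed, which the protocol does not state:

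- An exact one-sample binomial test of 0.775 against 0.50, two-sided 5%, needs 25 patients with hypotension (reject at 18 or more; upper-tail probability 0.0216; power 0.818).
- 25 / 0.7843 = 31.9, rounded up to 32.
- 32 / 0.90 = 35.6, rounded up to 36.

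This shows only that the figure can be reached with no agreement quantity in it. It does not establish how the calculation was actually run, and the point does not rest on it.

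**3. Why the three repeats cannot stand in**

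For one reading in a given patient, write

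reproducibility variance = σ_w² + σ_c²,

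where σ_w² is the variance among repeats within one examination and σ_c² is the variance added by changing operator or occasion. If the three readings come from one operator in one examination, any operator or occasion effect is common to all three and cancels from their differences. Their spread then estimates σ_w² alone. Since σ_c² ≥ 0, the underlying within-examination figure can only look as good as, or better than, true reproducibility. The protocol gives no value for σ_w² or σ_c², so the size of the gap cannot be worked out from it.

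**The case against.** **The operator is not stated, so the three readings might come from different people.** This stands as far as it goes. That the repeats form a single examination is inferred from the order of the steps. A reader might infer that the study will certainly yield no reproducibility data, but the text does not support that. What it supports is that the protocol does not provide for such data. If three operators taking one reading each were intended, the protocol would have to say so. Pure repeat error could then not be separated from differences between operators that vary from patient to patient, so the repeatability part would be left short instead.

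**The term is not defined and may be used loosely.** That is possible. Listing it separately from repeatability, twice, favours the standard meaning. If it is only a synonym, the word adds nothing and should go. If the reproducibility of the prediction is meant, index values under changed conditions are still needed.

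**This belongs in an analysis plan.** The choice of statistic does. The taking of readings does not.

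**Little else depends on it.** This is correct. The sample size, the cut-off and the secondary aim do not use reproducibility, which limits the weight of the point.

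**Further inferences that the document does not support.** A reader might put a percentage on how far repeatability would flatter reproducibility. Any such figure would rest wholly on an assumed variance ratio, and it would also differ between a single reading and the mean of three that the protocol uses. A reader might also conclude that the single readings are discarded because only the average is mentioned. The protocol does not say so. Data go into a registration form ("imaging, ECG and echocardiographic data will be obtained and recorded in special registration form") that is not shown.

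**Conclusion.** The point holds in limited form. Reproducibility is part of the stated primary aim, and the described design does not provide for the data needed to answer it. The only size that the document supports is a count: no described procedure gives readings under changed conditions.

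The conclusion rests on the standard measurement meaning of reproducibility. The warning against reporting agreement among the three readings as reproducibility also rests on those readings belonging to one examination, which is inferred and not stated.

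A reader might infer that the accuracy results or the comparison of the two indices are weakened. They are not, since neither needs readings under changed conditions. The text should be corrected, but this is no threat to the rest of the study.

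**What to change.** Remove reproducibility from the primary aim under 2. AIM/OBJECTIVES and from the matching sentence in the opening summary. Only if different operators or occasions are already intended, keep the word and state in Study Procedure who re-measures, when and in which patients. Whichever applies, do not report agreement among the three readings as reproducibility.

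The cost of removal is a minor amendment to the stated primary aim, possibly with notice to the ethics committee, since the protocol makes "Approval from the research Ethics committee of faculty of medicine" mandatory. The study would also claim less than it does now. No extra scans or staff are needed. Adding a second operator solely to keep the word would need extra resources and is not what is recommended here.

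### n = 32 gives 80% power for sensitivity only; about 7 patients are left to estimate specificity, whose power is about 4% against 50%

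*Protocol*

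**What the plan says.** The Sample Size Calculation in section 3 (Methodology) is a single chain. It opens with "Using PASS 11 program for sample size calculation", "setting power at 80"% and an error of 5%. It then takes "incidence of hypotension among patients undergoing general anesthesia at 78.43"% and "sensitivity and specificity of ultrasound guided Aorto-Caval index (IVC-AO) for prediction post general anesthesia hypotension at 77.5% and 63.6"%, and concludes "so a sample size of 32 patients undergoing craniotomy surgeries under general anesthesia will be needed". Dropout is added next: "Assuming that a drop out is of 10% , a sample size of at least 36 patients". A later line in the same section lists 40 cases.

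The paragraph gives no null value, no sidedness and no expected number of patients without hypotension. It does not say whether the 80% applies to sensitivity, to specificity or to both.

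The primary aim in section 2 is "Assessment of the accuracy, repeatability, and reproducibility of preoperative evaluation of IVC collapsibility index and Caval Aorta Index for prediction of hypotension". It names two indices. The calculation uses figures for the IVC/Ao index only.

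**The concern.** Sensitivity is estimated in patients who become hypotensive and specificity in those who do not. With an assumed incidence above 78%, a total of 32 splits very unevenly, so one sample size cannot be expected to serve both measures. The paragraph lists both as inputs to one power statement, and a reader will take 32 as adequate for both.

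Accuracy is the primary aim, and specificity is half of it. The optimal cut-off that section 3 also seeks trades sensitivity against specificity, so it depends on the same few normotensive patients. If they number about 7, the study cannot tell whether an index correctly clears patients who will stay normotensive, yet the protocol implies that it can.

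**Working it through.** **Inputs from section 3 of the protocol:** power 80%; error 5%; incidence 78.43%; sensitivity 77.5%; specificity 63.6%; n = 32; dropout 10%; at least 36 after dropout; 40 cases listed.

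**Assumptions, not in the protocol:** null value 50%; exact binomial test, two-sided at 5%.

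**1. Reproducing the stated 32 (sensitivity)**
- The smallest number of hypotensive patients giving at least 80% power for 77.5% against 50% is 25. The test rejects upward at 18 or more of 25, its actual two-sided size is 0.043, and its power is 0.818.
- Total: 25 / 0.7843 = 31.9, rounded up to 32. This is the protocol's figure.
- Dropout: 32 / 0.9 = 35.6, rounded up to 36. This also matches.

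Sensitivity against 50% therefore accounts for the stated sample size, without any use of the specificity.

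**2. Patients left for specificity**

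The share without hypotension is 1 − 0.7843 = 0.2157. This step needs no assumed null.
- 32 evaluable: 32 × 0.2157 = 6.9
- 36 evaluable: 36 × 0.2157 = 7.8
- 40 evaluable: 40 × 0.2157 = 8.6

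**3. Power for specificity 63.6% against 50%**

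With 7 patients the two-sided test rejects only at 7/7 or 0/7. Power = 0.636^7 + 0.364^7 = 0.0421 + 0.0008 = 0.043.

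| Patients without hypotension | Exact two-sided | Exact one-sided | Normal approx., two-sided | Normal approx., one-sided |
|---|---|---|---|---|
| 7 | 4.3% | 4.2% | 9.9% | 16.8% |
| 8 | 2.7% | 14.9% | 10.8% | 18.1% |
| 9 | 10.7% | 10.5% | 11.7% | 19.5% |

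The exact figures do not rise steadily because the rejection region changes in whole patients. The normal approximation is unreliable at these sizes and is shown only as an upper range. If the number without hypotension is allowed to vary binomially at n = 32, the average exact two-sided power is 4.4%.

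**4. Sensitivity to the assumed null (exact two-sided)**
- 7 patients: 21% against a null of 30% or 40%; 50% against 20%; 77.6% against 10%.
- 9 patients: 80.4% against 20%.

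**5. Precision, with no null at all (exact 95% intervals)**
- 4/7: 18.4% to 90.1%
- 5/7: 29.0% to 96.3%

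**6. Size needed for 80% power on specificity against 50%**
- Normal approximation: (1.96 × √(0.5 × 0.5) + 0.842 × √(0.636 × 0.364))² / (0.636 − 0.5)² = 103.7, so 104 patients without hypotension. In total 103.7 / 0.2157 ≈ 481.
- Exact test: power first reaches 80% at 110 (110 / 0.2157 ≈ 510 in total) and stays at or above it from 117 (117 / 0.2157 ≈ 542).

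**The case against.** The strongest reply is that the protocol never states a test of specificity against 50%. It gives no null, and what section 3 describes is strength of association and an optimal cut-off. On that view the 4% belongs to a test supplied by the review. A null of 50% for sensitivity, which the match at 32 supports, does not show that specificity was meant to be tested the same way. It can also be said that the paragraph only lists inputs and never claims 80% power for specificity in so many words.

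Part of this stands. The 4% is conditional on the assumed null and the exact two-sided test, and must be quoted with that condition. A low enough null changes the answer: with 9 patients, power against 20% is 80.4%. But 9 requires essentially all 40 patients to be evaluable, while the plan's own 10% dropout leaves 36 of 40. A null specificity of 20% or lower is also a weak benchmark for a predictor. The count of about 7 and the 18–90% interval depend on no null. As for the wording, a power statement that takes specificity as an input and does not say that it is unpowered will be read as covering it.

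Two smaller points are fair. The listed 40 does not contradict a minimum of 36, so it is no error. And 25 is a favourable point on the exact power curve, because power at 26 hypotensive patients falls to 78.6%. The required size for specificity on that same first-crossing basis is 110, not 117.

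**Conclusion.** The point holds. The protocol's 32 reproduces from sensitivity of the IVC/Ao index alone, and the protocol's own incidence leaves about 7 patients for specificity, or 8 to 9 at 36 to 40 evaluable. Against a null of 50%, exact two-sided power for specificity is about 3% to 11% over that range. One-sided tests and normal approximations stay below 20%. Powering specificity on the same basis would need about 480 to 540 patients, roughly fifteen times the planned number (481/32 = 15.0; 542/32 = 16.9).

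The 50% null, the sidedness and the exact test are assumptions. The count of patients without hypotension is not, and neither is the width of the interval it produces. The second index in the primary aim, IVCCI, has no sizing at all. The power statement is wrong as written for part of the primary aim and should be corrected.

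**What to change.** Restate the Sample Size Calculation in section 3 as follows:
- Say that 32 evaluable patients give about 80% power for sensitivity of the IVC/Ao index only, 77.5% against a stated null (50% reproduces the figure) in an exact two-sided 5% test. The 81.8% assumes exactly 25 hypotensive patients; averaged over the random number of events it is about 76% at 32 and about 82% at 36.
- Say that specificity of the IVC/Ao index, and all accuracy measures for IVCCI, are estimated with exact 95% intervals and are not powered.
- Give the expected number without hypotension (about 7 at 32 evaluable, 8 to 9 at 36 to 40) and the expected width, for example 18–90% for 4 of 7.
- Remove any implication that the 80% covers specificity.

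As an optional clarification, name one enrolment target in place of the two figures now given.

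The cost is protocol wording and a less favourable power claim. No patients are added and the study procedures do not change.

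### The stated 80% power can hold only for sensitivity, not for specificity, and the enrolment figures of 36 and 40 need to be reconciled

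*Protocol*

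**What the plan says.** Under Methodology, Sample Size Calculation, the protocol reports a calculation "setting power at 80% , error at 5" per cent. It uses "incidence of hypotension among patients undergoing general anesthesia at 78.43" per cent and "sensitivity and specificity of ultrasound guided Aorto-Caval index (IVC-AO) for prediction post general anesthesia hypotension at 77.5% and 63.6" per cent, and concludes "so a sample size of 32 patients undergoing craniotomy surgeries under general anesthesia will be needed". It then inflates for loss: "Assuming that a drop out is of 10" per cent, "a sample size of at least 36 patients undergoing craniotomy surgeries under general anesthesia will be needed".

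After the ethics items, a separate Sample size bullet gives 40 cases, with no derivation and no link to 36. The Study Period item says "the study will take place till reaching the target sample size" and does not say which figure is the target.

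The protocol does not state the null value, whether the test is one- or two-sided, or which of the two accuracy measures determines the 32.

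**The concern.** Two things in the same section need correcting.

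First, the calculation ends at a minimum of 36 and the Sample size bullet says 40. Since the study ends when the target is reached, the document should give that target one value.

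Second, and more important, one power figure is attached to two accuracy measures that rest on different patients. Sensitivity is estimated only in those who become hypotensive and specificity only in those who do not. With an expected incidence of 78.43%, nearly four in five patients inform sensitivity and about one in five informs specificity. Anyone reading the paragraph would take the study to have 80% power for both. The primary aim is the accuracy of the indices for prediction, so a reader would also expect specificity to be supported by the stated size.

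**Working it through.** **Inputs from the protocol:** power 80%, error 5%, incidence 78.43%, sensitivity 77.5%, specificity 63.6%, 32 evaluable, dropout 10%, enrolment at least 36 and 40.

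**Assumed, because not stated:** a one-sample exact binomial test with a null of 50%. One- and two-sided results are both shown, and other nulls are tried.

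**1. Reproducing 32 and 36.** For sensitivity 77.5% against 50%, two-sided 5%, the smallest number of hypotensive patients with at least 80% power is 25. The test rejects at 18 or more of 25, actual alpha is 0.043, and P(X ≥ 18 | 25, 0.775) = 81.8%. Then 25 / 0.7843 = 31.9, so 32, and 32 / 0.9 = 35.6, so 36. Both stated figures follow.

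The same two-sided calculation with other nulls does not give 32:
- 45% needs 20 events: 20 / 0.7843 = 25.5, so 26.
- 55% needs 37 events: 37 / 0.7843 = 47.2, so 48.

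One-sided at 50% needs 21 events: 21 / 0.7843 = 26.8, so 27. Two-sided at 50% is therefore a plausible reconstruction, though not the only conceivable one.

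**2. Sensitivity at the two enrolment figures** (null 50%). The number of hypotensive patients is not fixed in a cohort, so the averaged rows weight exact power over a binomial number of events, with 10% random dropout.

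| Basis | 36 enrolled | 40 enrolled |
|---|---|---|
| Events at expectation (25 and 28), two-sided | 81.8% | 84.1% |
| Averaged, two-sided | 76.7% | 81.6% |
| Averaged, one-sided | 86.2% | 89.9% |

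Averaged two-sided power is 89.9% and 93.1% against a null of 45%, and 57.9% and 64.8% against 55%.

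**3. Patients available for specificity.** The expected non-hypotensive number is n × (1 − 0.7843):
- 32 × 0.2157 = 6.9
- 36 × 0.2157 = 7.8

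**4. Power for specificity 63.6% against 50%.**
- With 7 such patients, only 7 of 7 is significant, because 6 or more of 7 has null probability 8/128 = 0.0625. Power is 0.636^7 = 4.2% one-sided, and 4.3% two-sided after adding 0.364^7.
- With 8, the two-sided test needs 8 of 8 (or 0 of 8), since 7 or more has two-sided probability 18/256 = 0.070. Power is 0.636^8 + 0.364^8 = 2.7%. The one-sided test rejects at 7 or more (9/256 = 0.035), with power 14.9%.

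Averaged over the binomial number of non-hypotensive patients:

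| Null for specificity | 32 evaluable, two-/one-sided | 36 evaluable, two-/one-sided |
|---|---|---|
| 50% | 4.4% / 8.1% | 5.3% / 9.4% |
| 40% | 12% / 24% | 15% / 27% |
| 30% | 27% / 42% | 33% / 48% |
| 20% | 55% / 65% | 62% / 70% |
| 10% | 79% / 85% | 84% / 89% |

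So 80% is reached only against a null somewhere between 10% and 20%. The normal approximation at 50% gives about 10 to 11% two-sided and 17 to 18% one-sided, which is still far short.

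**5. Scale.** By normal approximation, 80% power for specificity against 50% needs [z_α × 0.5 + 0.8416 × √(0.636 × 0.364)]² / 0.136² non-hypotensive patients. That is 81.4 one-sided (z_α = 1.645) and 103.7 two-sided (z_α = 1.960). Dividing by 0.2157 gives about 378 and 481 evaluable patients.

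**6. Precision.** If 5 of 8 non-hypotensive patients were classified correctly (62.5%), the exact 95% interval would run from about 24% to 91%.

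**The case against.** The strongest reply on the two figures is that they do not conflict: at least 36 is a floor, 40 meets it, and the bullet headed Sample size gives 40. That stands. Naming one target is a small reconciliation.

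A reader might infer more, and the documents do not support it:
- *That only 40 delivers 80% power.* On the calculation that reproduces 32, the step to 36 is the correct inflation for 10% dropout, and both sizes exceed 80%. Enrolling 36 falls short and 40 does not only with a two-sided exact test, an assumed null of 50%, and averaging over a random number of events. One-sided, both pass. Against 45% both pass, and against 55% both fail.
- *That 32 evaluable patients suffice only if exactly 25 become hypotensive.* Exact power moves in a saw-tooth: 78.6% at 26 events and 75.2% at 27, but above 80% for every count from 28 to 32.
- *That dropout was applied twice.* 36 / 0.9 does equal 40, but rounding up fits equally well.
- *That recruitment might stop at 36 or 40 according to the results.* The protocol describes no interim look, so this is conjecture.

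On specificity, it can be said that the protocol never expressly claims 80% for it, and that a separate null may have been entered in the software. The null is indeed unstated. But specificity is listed as an input to the single power statement with nothing to limit it, and the only nulls that would rescue the claim lie far below 50%.

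**Conclusion.** The point holds as a correction to how the power is stated, with a minor reconciliation of the enrolment figures. The arithmetic from 32 to 36 is right, and sensitivity is reasonably supported at either size. Specificity is not: about 7 to 8 informative patients and about 4 to 5% power two-sided, or 8 to 9% one-sided, against 50%. Choosing 40 over 36 makes almost no difference to that.

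The sensitivity figures rest on the assumed null of 50% and on the sidedness. The conclusion on specificity does not depend on that exact null: against 30%, averaged power is still only 27 to 48%. It does rest on the protocol's own 78.43% incidence, which fixes how few patients remain non-hypotensive.

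**What to change.** - Give 40 as the single enrolment target (40 × 0.9 = 36 evaluable) in both the Sample Size Calculation and the Sample size bullet. Keep 36 only as the minimum that the calculation produced, if at all.
- In Study Period, tie the end of recruitment to that figure.
- Have the sponsor state the null value and sidedness actually used. The 50% null here is a reconstruction and should not be written in as the design unless the sponsor confirms it.
- State that the 80% power applies to sensitivity only, and that specificity will be reported as an imprecise estimate with its confidence interval from an expected 7 to 8 non-hypotensive patients.

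The cost is a few sentences. No patients are added, because 40 is already a stated size.
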